3.2 Sample size

The study plans to recruit (signing of informed consent form) approximately 158 subjects at no more than 8 sites in China in order to include 142 subjects (284 eyes). It is expected that 127 subjects (254 eyes) will complete the study.

According to the CSRs summarized in PanOptix DL Response for China registration, the ocular SAE rate is 1.80%. A sample size of 127 subjects would ensure more than a 90% probability of observing at least one AE for any event that has a true incidence of 1.8% or greater.

Allowing for a 10% screening failure rate, approximately 158 subjects will be enrolled to obtain about 142 subjects who will undergo IOL implantation in both eyes. Assuming a further 10% dropout rate at Month 12 of follow-up, it is expected that 127 subjects (254 eyes) will complete the study.

3.3 Report text

Please refer to Figure 7-1 Study Design Flowchart in the protocol for the trial flowchart.

3.4 Changes from the Protocol

Demographics and baseline characteristics in the protocol will be summarized using FAS and PP. In this analysis plan, only FAS will be used.

4.0 Planned Analysis

This section will record the analysis of all study plans in order. This section will include the interim analysis in the plan and the analysis of the final plan. All analysis of all plans will be implemented by the biostatistician of Kun Tuo after the SAP is authorized, the database is locked and subject eligibility is determined by the Sponsor.

This study will implement the following analyses:

- Interim Analysis
- Final Analysis

4.1 Interim Analysis

This study plans to conduct an interim analysis of all data 6 months after all subjects have their second eye implanted.

Version 1.0, Aug 27, 2021 7 / 17

Protocol number: ILH297-C004 Statistical Analysis Plan

4.2 Final Analysis

The final analysis of this project will be performed 12 months after all subjects are implanted with the second eye. Unless stated otherwise, all final planned analyses specified in this SAP will be implemented by the biostatistician of Kun Tuo.

5.0 Analysis Sets

5.1 Safety Set (SS)

The safety analysis set includes all subjects who have tried the implantation of the investigational intraocular lens (IOL) (successfully implanted or aborted after IOL contact with the eye).

5.2 Full Analysis Set (FAS)

The full analysis set (FAS) includes all subjects who have had the investigational IOL successfully implanted in at least one eye and have undergone at least one postoperative effectiveness assessment (BCDVA, UCDVA).

5.3 Per Protocol Set (PP)

The per protocol analysis set (PP) is a subset of FAS and excludes all data/subjects that have met any of the critical deviation or evaluability criteria identified in the DEP.

6.0 General Considerations

6.1 Reference Start Date and Number of Study Days

The number of study days will be calculated from the reference start date and be used to indicate the number of start/end days of the assessment and event.

The reference start date is defined as the date of the first treatment of the investigational device (that is, the day of surgery is Day 0), and will appear in the list of all assessment/event dates.

- If the event date is not earlier than the reference date:
 - Number of study days = (event date reference date) + 1
- If the event date is earlier than the reference date:

Number of study days = (event date-reference date)

If the event date is incomplete or missing, the date in the list will remain incomplete or missing, and the number of study days and any corresponding duration will be presented based on the filling method specified in Annex II (Specifications for Incomplete Dates).

Version 1.0, Aug 27, 2021 8 / 17

Protocol number: ILH297-C004 Statistical Analysis Plan

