7-14 days after surgery	Visit 2 (1 week)	Visit 2A (1 week)			
30-60 days after the second eye surgery	Visit 3A	(1 month)			
90-120 days after the second eye surgery	Visit 4A (3 months)				
180-210 days after the second eye surgery	Visit 5A (6 months)				
360-390 days after the second eye surgery	Visit 6A (12 months)			

^{*}Implantation in the second eye must be performed 7-28 days after implantation in the first eye.

Table 7-5 SCHEDULE OF VISITS

Visit	Visit 0 Pre-op	Visit 00: OP	Visit 1	Visit 2	Visit 00A: OP ²	Visit 1A	Visit 2A	Visit 3A	Visit 4A	Visit 5A	Visit 6A	Early Exit
Eye	Both eyes	First eye	First eye	First eye	Second eye	Second eye	Secon d eye	Both eyes	Both eyes	Both eyes	Both eyes	Not applicable
Number of days	Day -28- Day 0	Surger y	Day 1-2	Day 7-	Surgery	Day 1-	Day 7- 14	Day 30-60	Day 90-120	Day 180- 210	Day 360-390	Not applicable
Informed consent	X											
Demographics	X											
Medical history	X											
Concomitant medication	X	X ⁴	X ⁴	X ⁴	X ⁴	X ⁴	X ⁴	X ⁴	X ⁴	X ⁴	X ⁴	X ⁴
Inclusion/exclusion	X	X			X							
Urine pregnancy test ³	X										X	X
Anterior chamber depth*	X											
Axial length*	X											
Corneal curvature*	X											
Target (expected) residual refractive error (spherical and cylindrical)*	Х											
QUVID questionnaire	X									X	X	X
Corneal endothelial cell	X								X	X	X	

Visit	Visit 0 Pre-op	Visit 00: OP	Visit 1	Visit 2	Visit 00A: OP ²	Visit 1A	Visit 2A	Visit 3A	Visit 4A	Visit 5A	Visit 6A	Early Exit
Eye	Both eyes	First eye	First eye	First eye	Second eye	Second eye	Secon d eye	Both eyes	Both eyes	Both eyes	Both eyes	Not applicable
Number of days	Day -28- Day 0	Surger	Day 1-2	Day 7-	Surgery	Day 1-	Day 7-	Day 30-60	Day 90-120	Day 180- 210	Day 360-390	Not applicable
count												
Distance visual acuity												
Best corrected distance visual acuity	X ⁵			X			X	X	X	X ⁵	X ⁵	X^5
Intermediate visual acuity at 60 cm												
• Distance corrected intermediate visual acuity								X	X	X ⁵	X ⁵	
Near visual acuity at 40 cm									•	•	•	
• Distance corrected near								X	X	X ⁵	X ⁵	

Visit	Visit 0 Pre-op	Visit 00: OP	Visit 1	Visit 2	Visit 00A: OP ²	Visit 1A	Visit 2A	Visit 3A	Visit 4A	Visit 5A	Visit 6A	Early Exit
Eye	Both eyes	First eye	First eye	First eye	Second eye	Second eye	Secon d eye	Both eyes	Both eyes	Both eyes	Both eyes	Not applicable
Number of days	Day -28- Day 0	Surger y	Day 1-2	Day 7-	Surgery	Day 1-	Day 7-	Day 30-60	Day 90-120	Day 180- 210	Day 360-390	Not applicable
visual acuity									,			

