6.2 Baseline

The baseline is defined as the last non-missing measurement (including unscheduled measurements) taken before the reference start date. Adverse events and device deficiency on the reference start date will be considered post-baseline.

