6.3 Data on Repeated Tests, Unscheduled Visits and Early Withdrawal

The summary by visit generally only presents the data recorded by the routine visit. Unscheduled measurements are not included in the summary by visit. For repeated tests (with the same visit number), the latest available measurement for that visit will be used for the summary by visit. Data on early withdrawal is not included in the summary by visit. The list will include data on scheduled, unscheduled visits and early withdrawal.

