6.4 Appointment of visit windows

According to protocol version 2.0, the following table describes the visit window for this study.

Visit	EYE	Day
Visit 0 Pre-Op	Both eyes	Day -28-0
Visit 00 OP ¹	1st Eye	Surgery
Visit 1	1st Eye	Day 1-2
Visit 2	1st Eye	Day 7-14
Visit 00A OP ²	2nd Eye	Surgery
Visit 1A	2nd Eye	Day 1-2
Visit 2A	2nd Eye	Day 7-14
Visit 3A	Both eyes	Day 30-60(Post second eye implant)
Visit 4 A	Both eyes	Day 90-120(Post second eye implant)
Visit 5A	Both eyes	Day 180-210(Post second eye implant)
Visit 6A	Both eyes	Day 360-390(Post second eye implant)
Early Withdrawal	N/A	N/A

- Visit 00 (1st eye surgery) must occur within 28 calendar days from Pre-operative Visit (Visit 0).
- Visit 00A (2nd eye surgery) must be performed within 7 to 28 calendar days after Visit 00 (1st eye surgery).

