Appendix 2. Specifications for Incomplete Dates

The filled date is not displayed in the list.

Algorithm of adverse events during treatment

Start Date	End Date	Action
Found	Found	If the start date is < the date of investigational IOL implantation, it will
		not be considered as a TEAE
		If the start date is >= the data of investigational IOL implantation, it
		will be considered as a TEAE
	Incomplete	If the start date is < the date of investigational IOL implantation, it will
		not be considered as a TEAE
		If the start date is >= the data of investigational IOL implantation, it
		will be considered as a TEAE
	Loss	If the start date is < the date of investigational IOL implantation, it will
		not be considered as a TEAE
		If the start date is >= the data of investigational IOL implantation, it
		will be considered as a TEAE
Incomplete, but the known part	Found	Non-TEAE
shows that it is unlikely to be the		
same day or later than the start date		
of the investigational drug		N. True
	Incomplete	Non-TEAE
	Loss	Non-TEAE
Incomplete, it may be the same day	Found	If the end date is considered as the date of investigational IOL
or later than the start date of the		implantation, it will not be considered as a TEAE
investigational drug		If the end date is >= the data of investigational IOL implantation, it
		will be considered as a TEAE
	Incomplete	First, fill in the latest possible date as the end date (that is, if the day is
		missing, fill in the last day of the month, if both day and month are
		missing, fill in December 31 of the current year):
		If the end date is considered as the date of investigational IOL
		implantation, it will not be considered as a TEAE
		If the end date is >= the data of investigational IOL implantation, it will be considered as a TEAE
	Loss	Assumed it as a TEAE
	LUSS	Assumed II do d LEAE
1	Found	If the end date is considered as the date of immediational TO
Loss	round	If the end date is considered as the date of investigational IOL implantation, it will not be considered as a TEAE
		If the end date is >= the data of investigational IOL implantation, it
		will be considered as a TEAE
	Incomplete	First, fill in the latest possible date as the end date (that is, if the day is
	ancomplete.	missing, fill in the last day of the month, if both day and month are
		missing, fill in December 31 of the current year):
		If the end date is considered as the date of investigational IOL
		implantation, it will not be considered as a TEAE

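### SAP 6.1 names surgery Day 0 but its formula makes it Day 1, and SAP 6.2's date cut-off rejects a permitted same-day preoperative baseline

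*SAP*

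**What the plan says.** **Study day.** SAP 6.1 sets the reference start date as the "date of the first treatment of the investigational device (that is, the day of surgery is Day 0". For dates on or after it the rule is "Number of study days = (event date reference date) + 1" (the minus sign was lost when the text was read); for earlier dates nothing is added. The result will "be used to indicate the number of start/end days of the assessment and event".

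**Windows.** Protocol Table 3-1 also treats surgery as Day 0. The footnote to Table 7-4 states: "Implantation in the second eye must be performed 7-28 days after implantation in the first eye". SAP 6.4 counts Visits 3A to 6A from the second implant, so Visit 5A is "Day 180-210(Post second eye implant". Visits 1A and 2A belong to the second eye.

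**Baseline.** SAP 6.2 reads: "The baseline is defined as the last non-missing measurement (including unscheduled measurements) taken before the reference start date". Protocol Tables 3-1 and 7-4 and SAP 6.4 let Visit 0 run from Day -28 to Day 0, and the footnotes set a maximum gap to first surgery but no minimum. For IOP, Protocol VIII (1) 2.5 ties baseline to the moment of implantation, not to a calendar date. SAP 1.0 requires departures from the protocol to be listed. SAP 3.4 lists one only, the analysis set for demographics.

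**The concern.** SAP 6.1 contradicts itself within one section: a day labelled 0 cannot come out of a formula whose smallest value on or after the reference date is 1. A programmer must choose between label and formula. A reader comparing listed study days with the windows in SAP 6.4 would also see a shift that has nothing to do with late attendance.

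The baseline rule has a different fault. It compares dates, so a measurement taken on the morning of surgery counts as not before surgery. Where the screening visit falls on that day, a valid preoperative value is discarded. At stake are the change in endothelial cell count (planned in Protocol VIII (1) 2.5) and baseline BCDVA (SAP 10.0). Neither carries the star in Protocol Table 7-5 that allows results from before consent to be reused.

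**Working it through.** **Inputs.** Formula and reference date: SAP 6.1. Gap between surgeries: 7 to 28 days (Protocol Table 7-4, SAP 6.4). Windows: SAP 6.4. Implanted eyes: 284 (SAP 3.2). One reference date per subject is assumed, which is the natural reading of first treatment.

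**1. Day of surgery.** SAP label: Day 0. Formula: 0 + 1 = 1. The day before gives -1. Differences of -2, -1, 0, 1, 2 give study days -2, -1, 1, 2, 3. The stated Day 0 is not reproduced and cannot occur.

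**2. First-eye visits.** Listed day = window day + 1. Visit 1 (window 1-2) lists as 2-3; Visit 2 (window 7-14) lists as 8-15. Only the last day of each window lists outside it.

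**3. Visits 1A to 6A.** Listed day = window day + gap + 1, so the shift is 7 + 1 = 8 to 28 + 1 = 29.

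| Visit | Window | Listed, as written |
|---|---|---|
| 1A | 1-2 | 9-31 |
| 2A | 7-14 | 15-43 |
| 3A | 30-60 | 38-89 |
| 4A | 90-120 | 98-149 |
| 5A | 180-210 | 188-239 |
| 6A | 360-390 | 368-419 |

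Without the +1 the shift is still 7 to 28; Visit 5A, for example, would list as 187-238.

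**4. How often the listed day leaves the window.** Visits 1A and 2A always list outside. Visits 3A to 6A each have 31 window days and 22 possible gaps, so 31 × 22 = 682 combinations. A shift of s leaves 31 - s days inside. Summing over s = 8 to 29 gives 23 + 22 + ... + 2 = (23 + 2) × 22 / 2 = 275, and 275/682 = 40%. This counts combinations equally; it is not a forecast of visits.

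**5. What does not change.** SAP 6.3 says: "The summary by visit generally only presents the data recorded by the routine visit". Treatment-emergent status in SAP Appendix 2 is decided by date, for example "If the start date is >= the data of investigational IOL implantation". Neither uses the study-day number.

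**6. Baseline.** Visit 0 may fall on any of Days -28 to 0, which is 29 days. The rule needs measurement date minus reference date to be below 0, so 28 days qualify and Day 0 fails. A second-eye value taken between the two surgeries also fails, although that eye has not been operated on. Visits 1 and 2 examine the first eye only, so such a value would be unscheduled, a type that SAP 6.2 admits. Each Day 0 screen with no earlier usable value removes 2/284 = 0.7% of implanted eyes from the endothelial-count change.

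**The case against.** - **The reference could be per eye.** The protocol labels both surgeries Day 0. On that reading second-eye results shift by 1 only, and the loss of between-surgery values disappears. This is fair, but first-eye results at Visits 3A to 6A would still shift by 8 to 29, and the Day 0 contradiction and same-day exclusion would remain.
- **Two anchors can coexist.** A subject-level study day beside windows labelled as counted from the second implant is not itself an error, and no readable text uses study day to judge visit timing. This stands. Only the 1-day part of the shift comes from a contradiction.
- **A surgery-based day is already planned.** The SSI listing in SAP 11.2.2 includes days from surgery. This stands, although the readable text does not say which surgery. Listing shells are in a separate document.
- **Day 0 screening is largely hypothetical.** The protocol counts 11 hospital visits, which requires Visit 0 and Visit 00 to be separate, and arranges Visit 00 after eligibility is confirmed. This stands as to frequency, but the stated window permits Day 0.
- **IOP is little exposed.** Table 7-3 schedules it at all visits except the day of surgery, and it is starred for reuse. The two definitions would therefore seldom give different values, but SAP 1.0 still requires the difference to be listed.

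**Conclusion.** Minor. Two rules are wrong as written: the SAP 6.1 formula cannot give the Day 0 that it names, and the SAP 6.2 cut-off discards a valid value in a case that the windows allow. The unlisted IOP difference is a smaller, formal omission.

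A reader might infer that on-time Visits 1A to 6A would all be listed 8 to 29 days beyond their windows. The documents do not support that. The 8 to 29 is a shift in day number under a single reference date, and 40% of the gap and day combinations for Visits 3A to 6A still list inside. Nor do Month 6 or Month 12 summaries, treatment-emergent status or the sample size change.

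The baseline effect rests on a literal reading, on no earlier usable value being available, and on no overriding rule in SAP safety text that cannot be read here. The number of affected subjects is not stated and is probably small.

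**What to change.** 1. **SAP 6.1:** drop the +1, so that surgery is Day 0 as in Protocol Table 3-1 and the windows. Calling surgery Day 1 would remove the internal contradiction but would not match the windows.
2. **SAP 6.2:** define baseline per eye as the last non-missing measurement before implantation or attempted implantation in that eye, including same-day preoperative values. For binocular and subject-level measures, use the last value before the first eye's implantation.
3. **SAP 3.4:** list any IOP baseline difference that remains.
4. **Optional:** show days from second-eye surgery beside the study day for Visits 1A to 6A, and state which surgery the SSI listing counts from.

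The cost is SAP wording and a programming derivation. An eye-level surgery date must be carried beside the subject-level reference date. Visit 0 values are preoperative by label, but a same-day unscheduled value would need a time or a flag for before or after surgery.

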6.2 Baseline

The baseline is defined as the last non-missing measurement (including unscheduled measurements) taken before the reference start date. Adverse events and device deficiency on the reference start date will be considered post-baseline.

6.3 Data on Repeated Tests, Unscheduled Visits and Early Withdrawal

The summary by visit generally only presents the data recorded by the routine visit. Unscheduled measurements are not included in the summary by visit. For repeated tests (with the same visit number), the latest available measurement for that visit will be used for the summary by visit. Data on early withdrawal is not included in the summary by visit. The list will include data on scheduled, unscheduled visits and early withdrawal.

6.4 Appointment of visit windows

According to protocol version 2.0, the following table describes the visit window for this study.

Visit	EYE	Day
Visit 0 Pre-Op	Both eyes	Day -28-0
Visit 00 OP ¹	1st Eye	Surgery
Visit 1	1st Eye	Day 1-2
Visit 2	1st Eye	Day 7-14
Visit 00A OP ²	2nd Eye	Surgery
Visit 1A	2nd Eye	Day 1-2
Visit 2A	2nd Eye	Day 7-14
Visit 3A	Both eyes	Day 30-60(Post second eye implant)
Visit 4 A	Both eyes	Day 90-120(Post second eye implant)
Visit 5A	Both eyes	Day 180-210(Post second eye implant)
Visit 6A	Both eyes	Day 360-390(Post second eye implant)
Early Withdrawal	N/A	N/A

- Visit 00 (1st eye surgery) must occur within 28 calendar days from Pre-operative Visit (Visit 0).
- Visit 00A (2nd eye surgery) must be performed within 7 to 28 calendar days after Visit 00 (1st eye surgery).

6.5 Statistical test

No inference is made about the primary endpoints. Therefore, no hypothesis tests are formulated.

6.6 General Calculation

Continuous variables will be summarized using number of observations, mean, standard deviation (SD), median, minimum and maximum, as well as confidence interval (CIs) or confidence limit, as applicable.

Frequency and percentage are used for descriptive statistics of the categorical variables.

For quantitative measurements, the calculation of the baseline change is as follows:

Tested value of visit X – baseline value

Version 1.0, Aug 27, 2021 9 / 17

Protocol number: ILH297-C004 Statistical Analysis Plan

6.6.1 Rules for Calculating Precision (Number of Decimal Places)

- The mean, median, and CI precision are the precision of the original data +1. E.g., the original data is x.x. and the mean is x.xx.
- The precision of SD and SE is the precision of the original data +2.
- The min/max precision is the same as the original data.

7.0 Statistical Consideration

7.1 Covariate Adjustment and Factors Included in the Analysis

Not Applicable.

7.2 Multicenter Study

This study will be implemented by multiple investigators in multiple sites. Central factors are not considered in the analysis.

Site combination is not performed for the analyses in this study.

7.3 Missing Data

Missing values will not be processed in this study.

7.4 Examination of Sub-groups

No subgroup analysis will be performed in this study.

8.0 Output Presentation

Appendix 1 describes the specifications for presenting output data.

The template provided with this SAP describes the output presentation of this study, and the format and content of summary tables, figures and lists are provided by the biostatistician of Kun Tuo.

9.0 Distribution and Withdrawal

All subjects enrolled in this study who provided informed consent are included in the calculation.

Discontinuation of the trial and the reason for discontinuation before implantation of the lens, attempt to implant the lens, successful implantation of the lens, completion of the trial, discontinuation of the trial and the reason for discontinuation after implantation of the lens, the number and/or percentage of the enrolled subjects will be described.

In addition, based on the full analysis set, the number and percentage of subjects, the number and percentage of subjects with missing causes, and the number and percentage of subjects with non-missing data will be described in accordance with the first eye, second eye, and visit.

The number and percentage of subjects in each analysis set are summarized according to the first eye, second eye, all eyes, and all subjects.

Version 1.0, Aug 27, 2021 10 / 17

This document is copyrighted by Kun Tuo Medical Research and Development (Beijing) Co., Ltd., and unauthorized use, disclosure or reproduction in any form is prohibited.

The number and percentage of subjects undergoing IOLs implantation, the number and percentage of subjects with screening failure, the number and percentage of subjects with trial termination before lens implantation after passing screening, and the number and percentage of all subjects are summarized by the investigator.

10.0 Demographic and Other Baseline Characteristics

Demographic data and other baseline characteristics will be presented to FAS.

This study will report the following demographic and other baseline characteristics in terms of sample size, mean, median, standard deviation, maximum and minimum:

- Age (years)
- Anterior Chamber Depth (mm)
- Axial Length (mm)
- Corneal curvature (D) (corneal astigmatism (D)= abs(K₁- K₂))
- Monocular BCDVA (logMAR)
- Binocular BCDVA (logMAR)

The number and percentage of subjects will be described for:

- Age group (< 65 years old; ≥ 65 years old)
- Gender

11.0 Effectiveness Results

11.1 Effectiveness Analysis

This study defines 4 primary effectiveness endpoints
effectiveness endpoints will be statistically analyzed in the FAS and PP analysis sets.

The primary

11.1.1 Primary Effectiveness Endpoint

The primary effectiveness endpoints of this study include the following, with the Month 6 results as the most critical endpoints:

- Percentage of eyes with BCDVA equal to or better than 0.3 logMAR.
- Mean monocular and binocular BCDVA
- Mean monocular and binocular DCIVA(60cm)
- Mean monocular and binocular DCNVA(40 cm)

